7. STATISTICS

Primary analysis

The primary endpoint of this study is the correlation of the change in C5b-9 and the change in platelet count from baseline (T0) to 15 minutes after administration of protamine (T2). The analyzed study population will consist of all patients with available measurements necessary to assess the primary endpoint.

The two changes (C5b-9 and platelet count) are continuous variables and their correlation (Spearman's rank-order correlation denoted by ρ) will be assessed. Therefore, the hypotheses

$$H_0: \rho = 0 \quad \text{vs.} \quad H_1: \rho \neq 0$$

will be tested using the Spearman rank-order correlation test, i.e. the null hypothesis that the Spearman correlation is zero against the alternative that it is not equal to zero. As C5b-9 levels and platelet count are assumed to be predictive for the clinical course of the patients, the association with secondary endpoints will be assessed. Moreover, as C5b-9 and platelet count will be documented at the study time points T0 to T8, their evolution over time will be analyzed using a linear mixed-effects model.

Sample size estimation

To the best of our knowledge, no study is available reporting the association of complement activity and change of platelets in cardiac patients. However, Qin et al. (4) reported a strong correlation (Pearson's correlation coefficient) of $r=0.683$ between platelets (MPV/PTC ratio) and mtDNA levels in 68 patients who underwent CABG. As mtDNA levels are strongly associated with complement activation (9), we expect to observe a comparable correlation between the change of platelets and complement activation. Power analysis was performed to determine the sample size for Spearman's correlation using G*Power (version 3.1.9.2). Assuming an effect size corresponding to $r=0.683$, a sample size of 162 has a power of 95% to assess a significant difference from a large effect of $r=0.5$ with a type I error at a global 5% level (two-tailed). To account for drop-outs, a total of 190 patients will be included.

Secondary analysis

All secondary parameters will be summarized using descriptive statistics, i.e. no./total no. (%) for categorical variables and median (25th to 75th percentile) or mean (SD), however appropriate.

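### The 95% power at 162 patients is a Pearson figure presented as a Spearman one, and its planning value of 0.683 belongs to a different pair of variables; the justification needs rewriting, not the number of patients.

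*Protocol*

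**What the plan says.** All of this is in section 7 of the protocol.

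- **Primary analysis.** The two changes from T0 to T2 are correlated with Spearman's coefficient, and the test concerns "the null hypothesis that the Spearman correlation is zero against the alternative that it is not equal to zero".
- **Sample size estimation, source.** The protocol says it knows of no study of complement activity and platelet change in cardiac patients. It turns to a study that "reported a strong correlation (Pearson's correlation coefficient) of $r=0.683$ between platelets (MPV/PTC ratio) and mtDNA levels in 68 patients who underwent CABG".
- **Sample size estimation, transfer.** The step to the primary endpoint rests on a strong association between mtDNA and complement, from which the protocol concludes: "we expect to observe a comparable correlation between the change of platelets and complement activation". No coefficient is given for the association between mtDNA and complement.
- **Sample size estimation, calculation.** G*Power was used to "determine the sample size for Spearman's correlation". With 0.683 as the assumed effect, 162 patients are said to give 95% power to show a difference from 0.5, two-tailed at 5%. Enrolment is raised to 190 for drop-outs, which allows for 28/190 = 14.7% of patients not being evaluable.

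**The concern.** Two features of the paragraph do not fit the planned analysis.

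First, the coefficient. The calculation is named as a Spearman one and the planned test is Spearman's, but 162 is what the Pearson formula gives. Spearman's coefficient has a larger sampling variance on the Fisher z scale, so the same sample gives less power against the same reference.

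Second, the effect size. The 0.683 differs from the primary endpoint in its type (Pearson, not Spearman), in both variables (MPV/PTC ratio and mtDNA, not platelet count and C5b-9), and as reported it concerns levels rather than changes from baseline. The bridge is a qualitative statement. Two strong correlations that share a variable do not fix the size of the third.

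This paragraph is the only justification of the study's size. As written, its power figure does not describe the statistic that will be used, and it depends strongly on a value that was not estimated for this endpoint.

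**Working it through.** **Inputs** (protocol, section 7): alternative 0.683; reference 0.5; two-sided alpha 5%; n = 162; power 95%; source sample 68; null of the planned test 0. Bivariate normality is my assumption; the protocol does not state it.

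**1. Reproducing the stated figure (Pearson, Fisher z).**
atanh(0.683) = 0.8347; atanh(0.5) = 0.5493; difference 0.2854.
n = ((1.960 + 1.645)/0.2854)² + 3 = 162.5.
Power at 162 = Φ(0.2854 × √159 − 1.960) = 94.9%. With the small bias term r/(2(n − 1)) it is 95.01%, and 162 is the first n to pass 95%. A simulation gave 95.3%. The one-sided version gives n = 136 and does not match. The stated number is therefore a correct Pearson calculation.

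**2. The same comparison with a Spearman statistic.** Two variance approximations on the z scale were used, 1.06/(n − 3) and (1 + rho²/2)/(n − 3), plus simulation with critical values calibrated to size. The protocol does not say whether 0.683 and 0.5 are to be read directly as Spearman values or converted from Pearson by rho_s = (6/π)·asin(r/2), which gives 0.666 and 0.483. Both readings are shown.

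| Reading | Power at 162: 1.06 / 1 + rho²/2 / simulation | n for 95% (two formulas) |
|---|---|---|
| 0.683 vs 0.5, read as Spearman | 93.8% / 91.4% / 92.5% | 173 to 191 |
| 0.666 vs 0.483, both converted | 92.3% / 90.0% / 91.6% | 184 to 201 |

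Example for the first cell: Φ(0.2854 × √159/√1.06 − 1.960) = 93.8%. Converting only the alternative (0.666 vs 0.5) gives 84 to 87%, but that treats the two inputs differently and I do not rely on it.

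**3. Dependence on the borrowed value** (reference 0.5, n = 162).

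| Assumed r | Pearson power | Spearman power (two formulas, both readings) |
|---|---|---|
| 0.683 | 95% | 90 to 94% |
| 0.65 | 81% | 73 to 79% |
| 0.60 | 44% | 38 to 42% |
| 0.55 | 14% | 12 to 13% |

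The 95% confidence interval of 0.683 from 68 patients is tanh(0.8347 ± 1.960/√65) = 0.53 to 0.79, before any allowance for the change of variables.

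**4. The test that is planned (rho = 0).** Spearman power at 162 for 0.683 is essentially 100%; about 24 patients would give 95%. The value detectable with 162 patients is tanh((1.960 + z_power) × √(1.06/159)):

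- 80% power: tanh(2.802 × 0.0816) = 0.22
- 90% power: tanh(3.242 × 0.0816) = 0.26
- 95% power: tanh(3.605 × 0.0816) = 0.29

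**The case against.** The strongest reply is that the arithmetic is right and the primary test is safe. Both parts stand. The stated inputs give 162 by the Pearson formula, so a reader who infers a calculation error would be wrong: the method does not match its label. Because the hypothesis tested is rho = 0, the loss of about 1 to 5 points against 0.5 does not carry over to the planned analysis.

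A reader might also infer that 190 patients are too few. The documents do not support that. It would require the 0.5 comparison to be the primary test, which it is not. Even against 0.5, a requirement above 190 arises only under some of the readings (173 to 191 unconverted, 184 to 201 converted).

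A third tempting inference is that the true correlation must be lower than 0.683, because multiplying it by an mtDNA–complement correlation below 1 shrinks it. That product is valid only if mtDNA is the sole link. Section 1.1 of the protocol describes a direct interplay of complement, platelets and coagulation, and presents mtDNA as an additional factor. Without the restriction, an assumed mtDNA–complement correlation of 0.7 allows a third correlation anywhere from 0.683 × 0.7 ± √((1 − 0.683²)(1 − 0.7²)), that is −0.04 to 1.00. So 0.683 is neither implied nor excluded.

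Finally, the protocol is open that no direct data exist and words the value as an expectation. That makes it a disclosed assumption, but the 95% built on it still has no support from this endpoint.

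**Conclusion.** The point holds as a defect in the stated justification. The 95% at 162 patients belongs to a Pearson comparison with 0.5. For a Spearman statistic and the same reference it is about 90 to 94%, given bivariate normality and depending on the variance formula and on whether the inputs are converted. The 0.683 is an unsupported planning value for the C5b-9 and platelet changes, in either direction.

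The study's ability to run its primary test is not in question. Even for a true rho of 0.34, taken only as an illustration of a value far below 0.683, the planned test of zero has about 99% power at 162: Φ(0.3541 × √159/√1.06 − 1.960) = 99.1%.

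**What to change.** Keep 190 enrolled and 162 evaluable. In section 7, Sample size estimation:

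1. Remove the 95% claim, and remove the argument from mtDNA as the basis for the sample size.
2. State what 162 evaluable patients detect with the planned Spearman test of rho = 0, two-sided 5%: |rho| of about 0.22 with 80% power, 0.26 with 90% and 0.29 with 95%. Name the variance approximation (1.06/(n − 3)).
3. If the comparison with 0.5 is kept for any purpose, give its Spearman power as about 90 to 94% at 0.683, state the normality assumption and how the inputs are read, and show how power falls for smaller values, as in the second table above.

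The cost is one rewritten paragraph and, if the 0.5 comparison stays, a slightly less favourable figure. No extra patients are needed.

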8. ETHICAL, LEGAL AND ADMINISTRATIVE ISSUES

8.1. Good Clinical Practice and Declaration of Helsinki

The procedures set out in this study protocol are designed to ensure that the Sponsor and the Investigator abide the principles of the ICH guidelines on GCP (E6) recommended for adaptation on 1st of May 1996 by the ICH Steering Committee and the Declaration of Helsinki concerning the conduct, evaluation and documentation of the study.

8.2. Approval of the Study Protocol

Prior to study start, the study protocol and/or other appropriate documents will be approved by the appropriate ethics committee and competent authorities.

8.3. Obtaining Informed Consent

Latest at the day before surgery the patient will be informed about the aim of the study and the need of study related blood sampling and collection of routine laboratory measurements and clinical data.

The patient will be asked to agree on processing the data collected during their participation in the observational clinical study. The patient's decision will be recorded in the patient's medical file.

8.4. Confidentiality

All local legal requirements regarding data protection will be adhered to. All study findings and documents will be regarded as confidential. The Investigator and members of the research team must not disclose any information without prior written approval from the Sponsor.

The anonymity of patients participating must be maintained. Throughout documentation and evaluation, the patients will be recognized on CRFs and other documents by identification number. Documents that identify the patient personally (e.g., the signed informed consent) will be maintained confidential by the Investigator. The patients will be told that all study findings will be handled in strictest confidence.

8.5. Archiving of Study Records

Essential documents will be retained for a minimum of 10 years after completion or discontinuation of the study.

9. AMENDMENTS

After the protocol has been submitted to an ethics committee (EC), any substantial change will require a formal amendment. Once the study has started, amendments will be made only in exceptional cases. The ethics committees must be informed of all amendments.

10. SCORES

SOFA

The SOFA is a six-organ dysfunction/failure score which is daily assessed. Each organ is graded from 0 (normal) to 4 (the most abnormal), providing a daily score of 0 to 24 points. Single organ failure is defined as SOFA score >2 for one organ and multiple organ daily arises with at least 2 organ systems with >2 points.

EUROSCORE II

The abbreviation stands for European System for Cardiac Operative Risk Evaluation and calculate the estimated pre-operative mortality by using the following factors which can be seen in the graphic below.

EuroSCORE II

Patient Related Factors

- Patient Age (years): 18-95
- Gender: Male / Female
- Creatinine Clearance (ml/min) or Dialysis:

> 85	51 - 85	< 51	Dialysis
------	---------	------	----------
- Calculate Creatinine Clearance
- Extracardiac Arteriopathy: Yes / No
- Poor Mobility: Yes / No
- Previous Cardiac Surgery: Yes / No
- Chronic Lung Disease: Yes / No
- Active Endocarditis: Yes / No
- Critical Preop State: Yes / No
- Diabetes on Insulin: Yes / No

Cardiac Related Factors

- NYHA Class: I / II / III / IV
- CCS Class 4 Angina: Yes / No
- LV Function (EF):

< 21%	21 - 30%	31 - 50%	> 50%
-------	----------	----------	-------
- Recent MI: Yes / No
- PA Systolic Pressure (mm Hg):

< 31	31 - 55	> 55
------	---------	------

Operation Related Factors

- Urgency: Elective / Urgent / Emergent / Salvage
- Thoracic Aortic Surgery: Yes / No
- Weight of the Intervention: (see key below)

1	2	3	4
---	---	---	---
- 1. Isolated CABG 3. Two procedures
- 2. Single non CABG 4. Three + procedures

Tap Any Label For Definition

Estimated Mortality:

Calculate Risk

Add to Database **Stored Patients** **Email Patient Data**

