2.2. Further Study Objectives

A secondary aim of the study is to investigate the specific pathway of complement activation, the mtDNA levels and the interaction with platelet function.

Therefore we search for correlations between levels of complement factors [c5b-9, C1q (C1r/C1s), C3a, C5a, MBL, Factor B, Factor D], mtDNA level [human NADH dehydrogenase 1 gene] and platelet function [MPV/PTC ratio and FACS for platelet activation factor 4 (PFA)].

Further it will be explored whether the level of complement activation and levels of mtDNA and the plasmatic coagulation system correlate with transfusion requirements, postoperative morbidity (need for revision surgery, cardiovascular events including thromboembolic events, sepsis, single or multiple organ failure according to SOFA Score), and in hospital mortality.

We will correlate levels of complement [see above] and concentration of coagulation factors [F I – F XIII, FXa, FXIIa, Kallikrein, Bradykinin, endogenous thrombin potential (ETP)] and transfusion requirements and correlate levels of complement, mtDNA and platelet function to postoperative morbidity (need for revision surgery, cardiovascular events including thromboembolic events, sepsis, single or multiple organ failure according to SOFA Score) and in hospital mortality.

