3.5. Secondary Study Endpoints

- levels of complement activation: c5b-9, C1q (C1r/C1s), C3a, C5a, MBL, Factor B, Factor D
- Levels of mtDNA
- platelet function as measured by FACS
- Levels of coagulation factors FI – FXIII, FXa, FXIIa, Kallikrein, Bradykinin, endogenous thrombin potential (ETP)
- transfusion requirements (red blood cell concentrates, fresh frozen plasma, platelet concentrate) and dosages of coagulation products administered during surgery, at ICU and until POD 3

- Need for revision surgery because of re-bleeding or hematoma formation **within** the first 24 hours at ICU
- hours/days on mechanical ventilation
- Oxygenation index (Horowitz quotient) during surgery, at ICU until POD 3 if applicable
- length of ICU stay
- length of hospital stay
- postoperative complications:
 - single and multiple organ failure according to SOFA score
 - acute kidney injury (RIFLE score)
 - diagnosed infection and sepsis
- incidence and type of cardiovascular thromboembolic events
- in hospital mortality

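### SOFA is named as an outcome only through an organ-failure cut; naming the highest total score as the variable for the secondary marker correlations would be a cheap improvement

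*Protocol*

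**What the plan says.** Section 10 of the protocol sets out the scale: "Each organ is graded from 0 (normal) to 4 (the most abnormal), providing a daily score of 0 to 24 points". It then defines the outcome: "Single organ failure is defined as SOFA score >2 for one organ", and multiple organ failure as two or more organs above the same grade.

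The Study Flow Chart schedules SOFA at T4, T5, T6, T7 and T8, with a footnote limiting it to patients still in the ICU. The score is therefore recorded up to five times per patient.

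As an outcome, SOFA appears in the synopsis, in section 2.2 and in section 3.5, each time as organ failure. Section 3.5 lists "single and multiple organ failure according to SOFA score". Section 2.2 plans to "correlate levels of complement, mtDNA and platelet function to postoperative morbidity", and organ failure by SOFA is one of the morbidity items it then names. None of these places names the total, the maximum or the change in SOFA.

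Section 7 summarises secondary parameters descriptively and leaves room for exploratory analyses of an open kind. It states no power, organ-failure rate or expected correlation for SOFA.

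**The concern.** The hypothesis in section 1.2 is about degree: more complement activation and more mtDNA should go with worse clinical outcome. The variable named for testing this discards most of the grading. A patient with six organs at grade 2 (6 × 2 = 12 points) is classed with a patient scoring 0, while a patient with one organ at grade 3 and the rest at 0 (3 points) is classed as a failure.

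Among the morbidity items that section 2.2 names for correlation, revision surgery, cardiovascular events, sepsis and death are events. SOFA is the one with an ordered scale behind it, and that scale is already being collected. If the association is graded and moderate, the cut could make a real relation look like none.

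**Working it through.** **Inputs from the protocol (section 7).** Two-sided 5% test, 162 evaluable patients, 190 enrolled ("To account for drop-outs, a total of 190 patients will be included"). These belong to the primary endpoint; the protocol sizes nothing for SOFA.

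**The plan's own figure.** Fisher z for r = 0.683 against 0.5 with 95% power:

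n = ((1.960 + 1.645) / (atanh 0.683 − atanh 0.5))² + 3 = 162.5.

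The stated 162 reproduces within rounding, with power 94.9% at 162. It also confirms that the test is two-sided, since a one-sided test would need 136. I use n = 162 and two-sided 5% below.

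**Assumed inputs.** Organ-failure rate p of 10%, 20% or 30%. Correlation r between marker and full score of 0.20 to 0.40. Marker and severity related in a graded, roughly normal way.

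**Attenuation from the cut.** Factor = φ(z_p) / √(p(1 − p)), where z_p is the normal quantile leaving p above it. The information kept is the factor squared.

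- p = 10%: 0.585, kept 34%, lost 66%
- p = 20%: 0.700, kept 49%, lost 51%
- p = 30%: 0.759, kept 58%, lost 42%

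**Power.** Φ(atanh(r × factor) × √159 − 1.960), with factor 1 for the full score. Example: r = 0.20 and p = 10% gives r × factor = 0.117 and power 31.7%.

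| r (full score) | Full score | Cut, p = 10% | Cut, p = 20% | Cut, p = 30% |
|---|---|---|---|---|
| 0.20 | 72.5% | 31.7% | 42.7% | 48.7% |
| 0.25 | 89.6% | 45.9% | 60.6% | 67.8% |
| 0.30 | 97.4% | 60.9% | 76.7% | 83.2% |
| 0.40 | about 100% | 85.2% | 95.2% | 97.7% |

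With all 190 patients the pattern is the same. At r = 0.20, 79% falls to 36%, 49% and 55%. At r = 0.30, 99% falls to 68%, 83% and 89%.

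**Where the loss is small.** At r = 0.40 it is 2 points with a 30% rate and 5 with 20%, but 15 with 10% and 32 with 5%. At r = 0.5 it is 3 points with a 10% rate and 14 with 5%.

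**Does a three-level grouping rescue it?** None, single and multiple can be kept as three ordered levels. If multiple failure is one third of all failure, the information lost is 65%, 48% and 37% at rates of 10%, 20% and 30%, against 66%, 51% and 42% for yes/no.

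**Check with six organ grades.** I also looked at simulated 0-4 grades for six organs (loading 0.6 on a common severity), tested by Spearman. Here r is the correlation of the marker with that underlying severity.

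- r = 0.3, 31% failure: total 88%, yes/no 59%, three levels 63%
- r = 0.3, 13% failure: total 85%, yes/no 42%, three levels 43%
- r = 0.2, 31% failure: total 54%, yes/no 31%, three levels 34%

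**The opposite model.** Suppose instead that the marker is raised by 0.7 SD only in patients with some organ above 2, and is otherwise unrelated to SOFA. Spearman power for the total against the three-level grouping is then 23-24% against 71-74% (10% rate), 50-58% against 93% (20%) and 71-76% against 97-98% (30%). The ranking reverses.

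**The case against.** The strongest case for leaving the text alone has five parts.

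- **The total score is not excluded.** A reader might infer that SOFA can enter the analysis only as a cut. The protocol does not say so. Section 10 defines organ failure, the flow chart schedules the score itself, section 7 leaves exploratory analyses open, and an analysis plan that is not shown could use the total. This stands: the point is limited to the outcomes that the protocol names.
- **The size depends on unstated inputs.** A reader might infer that the cut always costs half the information or 20 points of power. It does not. At a 30% rate the loss is 42%, and at r = 0.30 with that rate it is 14 points (97% to 83%). The figures are conditional.
- **The graded model favours the total.** Section 1.1 describes micro-thrombosis leading to organ failure, and an effect confined to overt failure would favour the cut, as the last calculation shows. The protocol does not settle which model holds. However, section 1.2 speaks of the degree of activation, so a graded analysis fits the stated hypothesis, and keeping the cut as a supporting analysis covers the other case.
- **Other graded outcomes exist.** Section 3.5 also lists ventilation time, the Horowitz quotient, lengths of stay and RIFLE. It would be wrong to say that SOFA is the study's only graded clinical outcome.
- **These analyses are secondary and carry no power claim.** This stands and limits the weight of the point.

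**Conclusion.** The point holds as a cheap improvement to secondary, exploratory analyses. The protocol names the coarser of two variables that it already collects, gives no reason for it, and states a hypothesis about degree.

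Under a graded relation at n = 162, the cut costs about 24 to 41 points of power at r = 0.20 and 14 to 37 points at r = 0.30 for failure rates of 30% down to 10%. The assumed rate, the assumed correlation and the graded shape all drive these figures, and none is given in the protocol.

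A reader might go further and conclude that the study is underpowered or its sample size wrong. The documents do not support that. The 162 and 190 rest on the primary correlation of C5b-9 change with platelet change, where SOFA plays no part, and no stated figure becomes wrong.

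**What to change.** In sections 3.5 and 10:

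- Name each patient's highest total SOFA over T4-T8 as the variable for the correlations with complement, mtDNA and platelet function, analysed by Spearman or an ordinal model.
- Keep single and multiple organ failure (organ grade above 2) as n/N (%) and as a supporting analysis.
- State how patients who leave the ICU before T8 are scored, since SOFA is calculated only in the ICU.
- If death is given the worst rank, do so only as a sensitivity analysis, because in-hospital mortality is already a separate endpoint.

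The cost is small: the scores are already scheduled, so no extra sample, visit or patient is needed, only revised wording, a rule for early ICU discharge and one more analysis per marker. There are two drawbacks. A correlation with a score is less directly clinical than an organ-failure rate. The maximum also rests on unequal numbers of ICU assessments, a problem that the organ-failure category partly shares.
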